2. INTRODUCTION AND OVERVIEW

This Statistical Analysis Plan (SAP) is based on protocol of study PTC-AADC-GT-002 entitled, “An Open Label Trial to Address the Safety of the Smartflow® MR-Compatible Ventricular Cannula for Administering Eladocagene Exuparvovec to Pediatric Subjects”, V11.0. This SAP provides more details for the statistical analyses specified in the study protocol.

2.1. Study Design

This is an open-label study in subjects with AADC deficiency. At minimum, 3 eligible pediatric subjects will be enrolled and receive eladocagene exuparvovec at 1.8×10^{11} vg via SmartFlow Magnetic Resonance (MR)-compatible ventricular cannula in a single operative session. Subjects will receive standard of care for their AADC deficiency during the study. Subjects will undergo Screening and a Baseline Visit before receiving eladocagene exuparvovec by intraputaminal infusion.

Subjects will return for regular visits during the course of the study. This study will have a Trial Phase, an Extension Phase, and a Long-Term Extension Phase. The length of the study, including the screening period, is 63 months (approximately 5 years).

The objectives of this study’s Trial Phase, Extension Phase, and Long-Term Extension Phase are as follows:

- The primary objectives of the Trial Phase are to assess the PD of eladocagene exuparvovec treatment by evaluation of HVA levels and to assess the safety of the SmartFlow MR-compatible-ventricular cannula for administering eladocagene exuparvovec to pediatric subjects with AADC deficiency. The secondary objectives of the Trial Phase are to further assess the PD of eladocagene exuparvovec in subjects with AADC deficiency using neurotransmitter metabolite assessment and PET analysis. The Trial Phase will be completed 8 weeks after administration of eladocagene exuparvovec.
- The Extension Phase is designed to capture additional clinical information for eladocagene exuparvovec through study evaluations, including changes in motor development, AADC-specific symptoms, and other PD measures. The Extension Phase will be completed at 48 weeks after administration of eladocagene exuparvovec.
- The Long-term Extension Phase is designed to capture long-term safety and efficacy data, for subjects treated with eladocagene exuparvovec, through Month 60.

A data safety monitoring board (DSMB) will conduct a formal review of safety data as outlined in the DSMB Charter. Review by DSMB will not be required to enroll successive subjects. The DSMB will monitor ongoing study results to ensure subject well-being, safety, and study integrity.

2.2. Study Objectives

2.2.1. Primary Objectives

The primary objectives are as follows:

- To assess the pharmacodynamics (PD) of eladocagene exuparvovec treatment by evaluation of homovanillic acid (HVA) levels at 8 weeks after administration

- To assess the safety of the SmartFlow MR-compatible ventricular cannula for administering eladocagene exuparvovec to pediatric subjects.

2.2.2. Secondary Objectives

The secondary study objectives are as follows:

- To assess the PD of eladocagene exuparvavoc by evaluating the following:
 - Homovanillic Acid (HVA) at Week 48
 - Positron emission tomography (PET) at Weeks 8 and 48
 - 5-hydroxyindoleacetic acid [5-HIAA] at Weeks 8 and 48
 - 3-O-methyldopa [3-OMD] at Weeks 8 and 48
- To evaluate the long-term efficacy of eladocagene exuparvavoc through Month 60 as assessed by the following:
 - Motor milestone attainment
 - Peabody Developmental Motor Scale, second edition (PDMS-2) score
 - Bayley Scale of Infant Development, third edition (Bayley-III)
 - EQ-5D-Y
 - Body weight
 - AADC-specific symptoms
- To evaluate the safety of eladocagene exuparvavoc treatment as assessed by treatment-emergent adverse events (TEAEs), neurological examinations, magnetic resonance imaging (MRI), and clinical laboratory tests.

2.3. Study Endpoints

2.3.1. Primary Endpoints

The primary efficacy endpoint is the change from baseline in HVA levels at the end of the Trial Phase (8 weeks after administration).

The primary safety endpoint is the assessment of adverse events (AEs) associated with the surgical administration of eladocagene exuparvovec to pediatric subjects using the SmartFlow MR-compatible ventricular cannula at the end of Trial Phase (8 weeks after administration).

2.3.2. Secondary Endpoints

The secondary endpoints are as follows:

- Change from baseline in neurotransmitter cerebrospinal fluid (CSF) metabolites HVA (at 48 weeks after administration),
- Change from baseline in PET imaging of putaminal-specific L-6-[¹⁸F] fluoro-3,4-dihydroxyphenylalanine (¹⁸F-DOPA) PET uptake at the end of the Trial Phase (8 weeks after administration) and the Extension Phase (48 weeks after administration).

- Change from baseline in neurotransmitter cerebrospinal fluid (CSF) metabolites 5-HIAA, and 3-OMD at 8 and 48 weeks after administration
- Attainment of motor milestones
- Motor development as assessed by the PDMS-2
- Cognitive and language development as assessed by Bayley-III
- Change in EQ-5D-Y
- Change in body weight
- Assessment of AADC-specific symptoms
- Overall safety profile characterized by type frequency, severity, timing, and relationship to study treatment of any TEAEs, neurological examination findings, brain imaging, or laboratory abnormalities.

2.4. Sample Size

The sample size is not based on statistical power consideration. A minimum of 3 subjects is planned to assess HVA levels at Week 8 and safety of the SmartFlow MR-compatible ventricular cannula for administering eladocagene exuparvovec to pediatric subjects.

3. ANALYSIS SETS

3.1. Pharmacodynamic Population

The PD population will consist of all subjects enrolled in the study who have received any amount of the study drug and have both baseline and at least one post-baseline value of at least one PD variable.

3.2. Safety Population

The safety population will consist of all subjects enrolled in the study who have received any amount of study drug.

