6. STUDY INTERVENTION DISCONTINUATION AND SUBJECT DISCONTINUATION/WITHDRAWAL

6.1. Stopping Rules

The procedure will be discontinued in the event of any occurrence that would potentially lead to intraoperative or postoperative complications or increased risk of subject harm.

At the subject level, the occurrence of any of the following events, regardless of causality, would lead to discontinuation of the procedure for any subject:

- Anesthesia complications
- Intracerebral hemorrhage demonstrated on imaging during the procedure
- Hemodynamic instability during the procedure
- Equipment malfunction
- Presence of a clinically significant CSF leak, in the opinion of the investigator, during the study procedure

At the study level, the occurrence of any of the following events, regardless of causality, would lead to halting of study enrollment:

- Any symptomatic intracerebral hemorrhage or stroke that results in a significant new neurologic deficit that persists one month following surgery
- Clinically significant CSF leak, in the opinion of the investigator
- Any central nervous system infections related to study interventions
- Dyskinesias severe enough to require intensive care unit (ICU) admission for greater than 30 days
- Any death

If any of these events occur, no further subjects will receive treatment until a comprehensive safety review has been completed by the DSMB and PTC. The United States Food and Drug Administration (FDA) and/or applicable country health authority(ies), Institutional Review Boards (IRBs), Institutional Ethics Committees, and the Institutional Biosafety Committee will be promptly notified.

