8.2. Subject Population(s) for Analysis

The following analysis population will be defined for the study:

Pharmacodynamic (PD) population: The PD population will consist of all subjects enrolled in the study who have received any amount of the study drug and have both baseline and at least one post-baseline value of at least one PD variable.

Safety Population: The safety population will consist of all subjects enrolled in the study who have received any amount of study drug.

Efficacy Population: The efficacy population will consist of all subjects enrolled in the study who have received any amount of the study drug and have both baseline and at least one post-baseline evaluation of at least one efficacy variable.

All analyses of PD variables will be based on the PD population. Evaluation of the safety variables will be based on the safety population, and all efficacy summary and analyses will be based on the efficacy population.

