8.3.2.2. Primary Safety Analysis

The primary safety analysis will focus on TEAEs that are defined as AEs with a start date after or worsen after receiving eladocagene exuparvovec.

The time of gene therapy administration will be the start time of the first infusion. All AEs reported will be coded using MedDRA. The number and proportion of subjects reporting TEAE will be summarized by System Organ Class (SOC) and by Preferred Term (PT) within SOC. Summaries will also be provided for each severity grade, relationship to cannula device, to gene therapy, and to neurosurgical procedure, and AEs of special interest.

Serious Adverse Events will be summarized using SOC and PT.

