3.3. Efficacy Population

The efficacy population will consist of all subjects enrolled in the study who have received any amount of the study drug and have both baseline and at least one post-baseline evaluation of at least one efficacy variable.

Analyses of pharmacodynamic variables, safety and tolerability variables, and efficacy variables will be based on the pharmacodynamic population, safety population, and efficacy population, respectively.

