7.1.1. Treatment-emergent Adverse Events

A TEAE is any AE that occurs post study drug administration. If onset date is missing, the AE is considered as TEAE.

An overall summary of TEAEs will be provided for number and percentage of subjects experiencing the following:

- TEAE.
- TEAE related to gene therapy.
- TEAE related to surgical device.
- TEAE related to neurosurgical procedure.
- TEAE related to F-DOPA.
- TEAE by severity.
- TEAE leading to withdrawal.
- TEAE of special interest (TEAESI: dyskinesia and cerebrospinal fluid leakage)
- Treatment emergent SAE (TESAE)
- TESAE and reasons for SAE
- TESAE related to gene therapy.

In the overall summary of TEAEs table, besides tabulating the number and percentage of subjects, the total number of TEAE episodes will also be provided. If a subject has repeated episodes of a particular TEAE, all episodes will be counted in the summary table.

Summary of number and percentage of subjects experiencing a TEAE will be presented for the following:

- TEAE by PT in descending order of incidence
- TEAE by SOC and PT
- TEAE related to gene therapy by SOC and PT.
- TEAE related to surgical device by SOC and PT.
- TEAE related to neurosurgical procedure by SOC and PT.
- TEAE related to F-DOPA by SOC and PT.
- TEAE by SOC, PT, and severity.

- TEAE leading to withdrawal by SOC and PT.
- TEAESI by SOC and PT.
- TESAE by SOC and PT
- TESAE related to gene therapy by SOC and PT

In the summary tables listed above, the percentage of subjects with TEAEs will be calculated by dividing the number of subjects who have experienced the event by the total number of subjects in the safety set. If a subject has repeated episodes of a particular TEAE, only the most severe episode, or the episode with the strongest causal relationship to study drug, will be counted in the summary tables.

A subject with more than one type of TEAE in a particular SOC will be counted only once in the total of subjects experiencing TEAEs in that particular SOC. Since a subject could have more than one type of TEAE within a particular SOC, the sum of subjects experiencing different TEAEs within the SOC could appear larger than the total number of subjects experiencing TEAEs in that SOC. Similarly, a subject who has experienced a TEAE in more than one SOC will be counted only once in the total number of subjects experiencing AEs in all SOCs.

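### The primary safety endpoint concerns the operation and the cannula, but its tables start at drug receipt, so adverse events before the first infusion are not counted

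*SAP*

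**What the plan says.** SAP 2.3.1 (and Protocol 2.3) defines the primary safety endpoint as the "assessment of adverse events (AEs) associated with the surgical administration of eladocagene exuparvovec to pediatric subjects using the SmartFlow MR-compatible ventricular cannula", to Week 8.

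The analysis set is tied to the drug. SAP 3.2: "The safety population will consist of all subjects enrolled in the study who have received any amount of study drug". Protocol 8.2 adds: "Evaluation of the safety variables will be based on the safety population". SAP 3.3 makes the same assignment: "safety and tolerability variables, and efficacy variables will be based on the pharmacodynamic population, safety population, and efficacy population, respectively".

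The event definition is also tied to the drug. Protocol 8.3.2.2 focuses on "TEAEs that are defined as AEs with a start date after or worsen after receiving eladocagene exuparvovec" and fixes the clock: "The time of gene therapy administration will be the start time of the first infusion". SAP 7.1.1 is shorter: "A TEAE is any AE that occurs post study drug administration". It adds that an AE with no onset date counts as treatment-emergent. Every summary listed in that section (device, neurosurgery, special interest, serious) is a TEAE table, and the by-term percentages are taken over the safety set.

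Protocol 6.1 lists five kinds of event, including hemorrhage seen on imaging, a significant CSF leak and equipment malfunction, that "would lead to discontinuation of the procedure for any subject". It does not say that infusion must have begun.

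**The concern.** Exposure to the surgery begins before exposure to the drug. Protocol Table 1 (footnote m) shows this: CSF is taken during the operation but before dosing. A bleed, leak or device failure at that stage is the kind of outcome that the primary safety endpoint exists to describe. If it stops the operation, the child never receives drug and leaves both numerator and denominator. If the operation goes on, the event may still fall outside the TEAE tables because it began too early.

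With a planned minimum of 3 children, one such event can decide whether a device or neurosurgery table shows zero.

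**Working it through.** There is no planned figure to reproduce. Protocol 8.1 and SAP 2.4 give a minimum of 3 subjects with no statistical basis, and neither document gives an expected rate of stopped operations or operative AEs. The check follows a child through the definitions, then illustrates the size.

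**Step 1. Stopped before the first infusion.**
- Drug received: none, so the child is outside the safety set (SAP 3.2, Protocol 8.2).
- TEAE: impossible, because no drug administration precedes the AE (SAP 7.1.1).
- AE summary tables: none. SAP 7.1 collects and codes all AEs from consent but names no summaries other than the TEAE tables.
- Elsewhere: the listing of all AEs (SAP 7.1.1) and the intrasurgical MRI listing of hemorrhage and leak (SAP 5.9). The disposition table (SAP 5.1) may show the child as not dosed or discontinued, but it has no AE count.

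**Step 2. Dosed, with an operative AE that began before infusion.**
- Protocol 8.3.2.2 applies: the AE is treatment-emergent only if it worsens after the first infusion starts.
- If it does not worsen, it is in none of the device, neurosurgery, special-interest or serious-event tables, and no other AE table is planned.
- Applying the rule on Day 1 needs an onset time. The recording list in Protocol 7.5.4 names the onset date and no time, and the SAP covers only a missing date. If the eCRF, which is not among the documents, holds only the date, the rule cannot be applied reliably to Day 1 events.

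**Step 3. Worsening.** Protocol 8.3.2.2 includes worsening after treatment. SAP 7.1.1 leaves it out, while SAP 4.4 declares no departure from the protocol analysis.

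**Not affected.** A child who received any drug before the stop is in the safety set, and infusion interruptions are tabulated (SAP 5.8). AEs known to start after the first infusion begins are counted.

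**Step 4. Illustration, with exact (Clopper-Pearson) 95% limits.** The SAP plans no intervals for these tables; they are shown only to indicate how little 3 or 4 children can tell. For 0/n the upper limit is 1 − 0.025^(1/n), so 0/3 gives 1 − 0.025^(1/3) = 0.708. For 1/n the lower limit is 1 − 0.975^(1/n), so 1/4 gives 0.006; its upper limit, from the beta distribution, is 0.806.

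| Assumed case | Planned table | All operations started |
|---|---|---|
| AE-caused stop beside 3 dosed, none with such an AE | 0/3 = 0% (0 to 71%) | 1/4 = 25% (0.6 to 81%) |
| Same, beside 10 dosed | 0/10 = 0% (0 to 31%) | 1/11 = 9.1% (0.2 to 41%) |
| Stop without an AE, beside 3 dosed, one with an AE | 1/3 = 33% (0.8 to 91%) | 1/4 = 25% (0.6 to 81%) |
| One of 3 dosed has a pre-infusion AE that does not worsen | 0/3 | 1/3 |

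**Step 5. How often might it arise?** With an assumed chance p of a pre-infusion stop per operation, the probability of at least one in n operations is 1 − (1 − p)^n.

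| Assumed p | n = 3 | n = 4 |
|---|---|---|
| 2% | 1 − 0.98³ = 5.9% | 7.8% |
| 5% | 1 − 0.95³ = 14.3% | 18.5% |
| 10% | 1 − 0.90³ = 27.1% | 34.4% |

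**The case against.** The best defence is that little is hidden. The study is descriptive, tests no safety hypothesis and may have only 3 children. Every AE is listed by subject, intrasurgical hemorrhage and leak have their own listing, and the Data Safety Monitoring Board evaluates all AEs (Protocol 7.5.12). The disposition table counts screened, failed and dosed subjects and gives discontinuation reasons by phase, so an operated but undosed child may be visible there. A drug-based safety set is also conventional, and the table shells are in a separate document (SAP 8).

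Most of this stands as a limit on the harm. It does not close the gap. Protocol 8.3.2.2 makes the number and proportion of subjects with events the primary safety analysis, and neither a listing nor a disposition count supplies that for the operation or the cannula.

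Two further objections narrow the point:
- A reader might infer that AEs before infusion on Day 1 have no classification rule at all. That is not so, since Protocol 8.3.2.2 sets the clock at the first infusion. Nor do the documents establish that onset time goes unrecorded. The list in Protocol 7.5.4 is not the whole AE form: it omits relationship to the cannula, which Protocol 7.5.5 requires.
- Worsening of a pre-existing illness is itself reportable as an AE (Protocol 7.5.2.1). The missing clause in the SAP therefore mainly affects AEs that began between consent and infusion.

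**Conclusion.** The mismatch is real and should be fixed. Followed as written, the plan leaves a child stopped before infusion out of every AE summary table. It also leaves operative AEs that began before infusion and did not worsen out of those tables in dosed children. Both conclusions follow from the definitions and need no assumed rate.

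The size does rest on assumption, since the stop rates and event patterns are illustrative. The intervals for 0/3 and 1/4 overlap almost entirely. A reader might infer that the plan always understates risk, but a stop without an AE raises the reported percentage by shrinking the denominator. A reader might also infer that such events vanish from the report; they remain in the listings. The Day 1 timing problem is conditional on what the eCRF records.

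**What to change.** - **Analysis set.** In SAP 3 and Protocol 8.2, add a procedure-started set: all subjects in whom the Day 1 procedure was started, dosed or not. Define the start point once, for example the start of anesthesia, so that two programmers cannot differ. Use this set for the device-related, neurosurgery-related, special-interest and serious-event tables of the primary safety endpoint.
- **Event window.** In SAP 7.1.1 and Protocol 8.3.2.2, for those tables, count AEs with onset or worsening from that start point. Count a Day 1 AE without an onset time as inside the window, in line with the SAP's rule for a missing onset date.
- **Drug-related tables.** Keep the present safety set and TEAE definition for gene-therapy-related tables, and restore the worsening clause in SAP 7.1.1.
- **Record.** Enter the changes in SAP 4.4 and add a disposition row in SAP 5.1 for procedure started but not dosed.

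A separate denominator of children in whom cannula insertion was attempted is optional. It would matter if a child were stopped before insertion: one cannula AE among 3 exposed children is 1/3 = 33%, against 1/4 = 25% over all operations started. It would need a site record of attempted insertion.

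The cost is wording, one more analysis set and one more AE window to program. AEs are already collected from consent (Protocol 7.5.8, SAP 7.1). AE percentages may move in either direction.

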3.3. Efficacy Population

The efficacy population will consist of all subjects enrolled in the study who have received any amount of the study drug and have both baseline and at least one post-baseline evaluation of at least one efficacy variable.

Analyses of pharmacodynamic variables, safety and tolerability variables, and efficacy variables will be based on the pharmacodynamic population, safety population, and efficacy population, respectively.

4. GENERAL CONSIDERATIONS

Unless otherwise specified, continuous variables will be summarized by presenting the number of non-missing observations, mean, standard deviation, median, minimum, maximum, 25th percentile and 75th percentile.

Categorical variables will be summarized by presenting the number of subjects and percentage for each category.

All lab values that are reported as “< LLOQ” will be displayed in the listings as received but for summary statistics, this will be imputed as 0.5*LLOQ. For other laboratory values recorded as “< x.x” will be imputed as “x.x” minus 1 or other reasonable handling method as suggested by clinician for calculation.

When appropriate, study days will be listed in the data listings. For each subject, study day is measured relative to the day of study drug administration.

When data are summarized by visit, it will be based on nominal visit as shown on the case report form (CRF), and no date window will be applied. The site will be instructed to complete all assessments required for each study visit according to the schedule of assessments.

Analyses will be performed using SAS for Windows statistical software, version 9.4 or higher (SAS, Cary, NC), except where other software may be deemed more appropriate.

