^p Complete physical examination at Screening, Baseline Visit, and on Dosing Day (D1), and targeted physical examination for all other visits. The complete physical examination will consist of an examination of the following: neurological assessment and assessments of general appearance, any changes to feeding tube placement or removal, skin, head, eyes, ears, nose, throat, neck (including thyroid), lymph nodes, chest, heart, abdomen, and extremities. The targeted physical examination will consist of a neurological assessment, general appearance assessment, any changes to feeding tube placement or removal, and heart auscultation.

^q Vital signs include temperature, pulse, respiratory rate, and blood pressure.

^r Brain MRI with gadolinium performed at Screening to exclude subjects who may have pre-existing conditions.

^s Brain MRI with gadolinium to check for persistent CSF leakage/fistula and inflammatory changes (eg, aseptic ventriculitis/meningitis). An MRI should be performed immediately if a CSF leak is suspected.

^t Brain CT for postdose hemorrhage check should be performed within 6 hours after the end of surgery.

^u PET scans will be centrally read.

^v P-A and lateral chest x-ray.

^w Parent/caregiver must complete eDiary or paper diary for each OGC occurrence throughout the Trial Phase and Extension Phase. In the event that the eDiary cannot be used, a paper version will be provided.

^x Findings for AADC-specific symptoms will be collected at every in-person visit after D1. These assess for floppiness (hypotonia), limb and stimulus-provoked dystonia, and muscle power.

^y Laboratory tests (PT; PTT or aPTT; INR; CBC w/diff; and CMP analysis [including total bilirubin]). These will be assessed by a local laboratory.

^z The EQ-5D-Y will not be administered to subjects under 4 years of age. If the subject turns 4 during the study, the caregiver will complete the EQ-5D-Y per protocol after the subject turns 4.

Table 2: Schedule of Events for Extension Phase

Visit	10	11	12	13	14	15	16	17	18	19	20
Type of Visit (In-Person or Phone)	Phone	In-Person	Phone	Phone	In-Person	Phone	Phone	In-Person	Phone	Phone	In-Person
Visit Window ^a	W10 ±2D	W12 ±3D	W16 ±2D	W20 ±2D	W24 ±3D	W28 ±2D	W32 ±2D	W36 ±3D	W40 ±2D	W44 ±2D	W48/ET ^b ±3D
Pregnancy Test ^c		X			X			X			X
CSF neurotransmitter analysis ^{d,e,f}											X
Anti-AAV2 antibody (IgG and neutralizing titers) ^d		X			X			X			X
Viral shedding (blood and urine) ^{d,g}	X			X			X				X

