7.2. Clinical Laboratory Tests

7.2.1. Chemistry

A summary table of descriptive statistics will be presented for the observed values and the change from baseline for chemistry parameters by time point. A listing of laboratory chemistry parameters will be provided.

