7.2.2. Hematology

A summary table of descriptive statistics will be presented for the observed values and the change from baseline for hematology parameters by time point. A listing of laboratory hematology will be provided.

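### The SAP's default for laboratory values recorded as `< x.x` subtracts 1 from the limit, which is negative for any limit below 1 and depends on the unit; the permitted clinician alternative is not pre-specified

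*SAP*

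**What the plan says.** SAP section 4 (General Considerations) has two rules for left-censored laboratory results.

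- Results reported as below the LLOQ are listed as received, "but for summary statistics, this will be imputed as 0.5*LLOQ".
- A second sentence begins "For other laboratory values recorded as" `< x.x` and sets them to the stated limit "minus 1 or other reasonable handling method as suggested by clinician for calculation".

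The second rule has no floor at zero, names no analyte or unit, and gives no criterion for when the alternative replaces the subtraction.

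The values feed numerical summaries. SAP 7.2.1 states: "A summary table of descriptive statistics will be presented for the observed values and the change from baseline for chemistry parameters by time point". SAP 7.2.2 does the same "for the observed values and the change from baseline for hematology parameters by time point", and SAP 7.2.3 follows the same pattern for the clotting tests and INR. None of the three sections limits or overrides the section 4 rule. Viral shedding (SAP 7.2.4) has its own rule: results below the limit of quantification or detection are classed as not detected.

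The panel is in a footnote to Table 1 of Protocol 7.1: "Laboratory tests (PT; PTT or aPTT; INR; CBC w/diff; and CMP analysis [including total bilirubin]). These will be assessed by a local laboratory". Neither document gives reporting limits or units for these tests.

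**The concern.** A concentration or count cannot be negative, yet the default produces a negative number for every limit below 1. It also has no fixed meaning across units: 1 is a large quantity for an analyte measured in tenths and a trivial one for an analyte measured in tens. The SAP's own LLOQ rule has neither problem, because it takes a constant proportion of the limit.

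At stake is the credibility of the laboratory tables. SAP section 4 asks for mean, standard deviation, median, minimum, maximum and quartiles, so a negative substitute could be printed directly as a minimum. It would also enter means and changes from baseline, where a small group gives it weight. Clinical laboratory tests are part of a secondary objective, and laboratory abnormalities are part of the safety-profile secondary endpoint.

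**Working it through.** **Inputs.** From SAP section 4: default substitute = L - 1 for a limit L, and LLOQ substitute = 0.5 × L. From SAP 2.4: a minimum of 3 subjects. The values of L below are assumptions chosen to show the range. The plan states no figure on this point, so there is none to reproduce.

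**Step 1: sign and size.** L - 1 < 0 whenever L < 1.

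| Assumed limit L | L - 1 | (L - 1)/L | 0.5 × L |
|---|---|---|---|
| 0.1 | -0.9 | -900% | 0.05 |
| 0.2 | -0.8 | -400% | 0.10 |
| 0.5 | -0.5 | -100% | 0.25 |
| 0.9 | -0.1 | -11% | 0.45 |
| 1.0 | 0 | 0% | 0.50 |
| 2 | 1 | 50% | 1.0 |
| 5 | 4 | 80% | 2.5 |
| 50 | 49 | 98% | 25 |

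The rules differ by (L - 1) - L/2 = L/2 - 1, so they agree only at L = 2. Below that, the default is lower than half the limit; above it, higher.

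**Step 2: unit dependence.** Multiply the limit by a conversion factor k, subtract 1 and convert back: (kL - 1)/k = L - 1/k. The result depends on k.

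- `<0.2` gives -0.8. In a unit ten times smaller (k = 10) it is `<2`, which gives 1, or 1/10 = 0.1 in the first unit.
- `<5` gives 4. In a unit ten times larger (k = 0.1) it is `<0.5`, which gives -0.5, or -0.5/0.1 = -5 in the first unit.

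Under the LLOQ rule, (0.5 × kL)/k = 0.5 × L for every k.

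**Step 3: effect on a visit mean.** One censored result among n subjects moves the mean, relative to half the limit, by (L/2 - 1)/n.

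- L = 0.2, n = 3: (0.1 - 1)/3 = -0.30.
- L = 0.5, n = 3: (0.25 - 1)/3 = -0.25.
- L = 0.2, n = 10: (0.1 - 1)/10 = -0.09.

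At n = 3 with L = 0.2, the shift exceeds the limit itself.

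**Step 4: effect on change from baseline.** Assume a baseline of `<0.2` and a follow-up value of 0.3. The default gives 0.3 - (-0.8) = 1.1. Half the limit gives 0.3 - 0.1 = 0.2. The default change is larger than the measured follow-up value.

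**The case against.** The strongest reply is that the same sentence allows another reasonable method, and a clinician shown a negative bilirubin would use it. That stands in part: negative values are the default result, not an inevitable one. A reader might infer that the tables will contain them, and the documents do not support that. But the clause names no method and no condition for using it, so it does not make the default acceptable.

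A second reply is that a local laboratory's `<0.2` may simply be its quantification limit, in which case the first rule applies and gives 0.1. The SAP does not say whether its LLOQ rule covers only results carrying that label or any result below a quantification limit. Some results may therefore escape the second rule. The author may also have meant one unit in the last decimal place, so that `<0.2` becomes 0.1, but the SAP does not say so.

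A third reply concerns consequence. The three sets of tables are descriptive, listings are planned beside them, and with few subjects an impossible value would be easy to spot. Protocol 7.5.2.1 separately requires laboratory abnormalities needing intervention or further investigation to be reported as adverse events, unless they belong to a clinical event already reported. All of this stands and limits the weight of the point.

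Three further inferences are tempting and not supported:

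- That the clinician would choose after seeing the results. The SAP gives no timing; the fair criticism is that the choice is not pre-specified.
- That CSF cell-count or protein tables would be distorted. These are collected, but the SAP's CSF summary (6.2.1) covers only 5-HIAA, HVA and 3-OMD.
- That the primary HVA result is affected. The words about other laboratory values are not confined to safety tests, but nothing in the documents shows that HVA would be reported in the second form.

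**Conclusion.** The rule is wrong as written, not merely incomplete. By arithmetic alone, the default is negative for every limit below 1 and varies with the unit, and nothing in SAP 7.2.1 to 7.2.3 corrects it. The clinician alternative might avoid the error, but it is unspecified.

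The practical size is conditional. It requires a result that falls under the second rule, a limit well away from 2, and use of the default. The documents give no limits or units, so the frequency cannot be estimated and the examples are illustrations. Where the conditions are met, the distortion is noticeable at the planned minimum of 3 subjects and shrinks in proportion to 1/n. It is confined to means, minima and changes from baseline in the descriptive chemistry, hematology and coagulation tables. This is a modest point, worth correcting because the rule is plainly faulty and the correction is nearly free.

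**What to change.** In SAP section 4, replace the subtraction with the SAP's own proportional rule: every laboratory result recorded as `< x.x` and summarized numerically is set to 0.5 times the reported limit, whether or not that limit is labelled an LLOQ. This also removes the need to decide which of the two rules a given result falls under. State that these results, too, are listed as received.

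If a clinician wants different handling for an analyte, name the analyte and the method in the SAP before the affected summaries are produced. Keeping the clause in that pre-specified form is enough; it need not be deleted.

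The change removes negative values and unit dependence. It does not remove differences between laboratories with different limits: `<0.2` would give 0.10 and `<0.5` would give 0.25. The listings should keep the reported limits visible for that reason.

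The cost is one SAP sentence and one line of programming, plus a short list of exceptions if any are wanted. No data collection changes.
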